### 5.2.2 Exclusion Criteria

- Motor Neurone Disease syndromes that do not have clinically detectable Upper Motor Neurone signs (e.g., flail arm or flail leg onset of ALS)
- A clinical diagnosis of dementia as determined by the Investigator.
- Current treatment with anticoagulants (e.g., warfarin, novel oral anticoagulants, heparin) that might preclude safe completion of the lumbar puncture.
- Condition that precludes the safe performance of routine lumbar puncture, such as prohibitive lumbar spinal disease, bleeding diathesis, or clinically significant coagulopathy or thrombocytopenia.
- Use of investigational drugs or devices within 60 days prior to baseline (dietary supplements taken outside of a clinical trial are not exclusionary, e.g., coenzyme Q10).

- Prolonged prothrombin time or activated partial thromboplastin time >2xULN
- Severe hypertension or hypotension
- Glomerular filtration rate (GFR) <35 mL/min
- Prior exposure to any exogenous form of APC
- FVC at screening of <50% of predicted
  - *Participants who fail to meet this criterion due to technical difficulties may be considered at the Principal Investigator's discretion.*
- Inability to lie flat for investigational procedures (MRI, PET, Lumbar Puncture)
- Previously obtained MRI scan with evidence of clinically significant neurological disorder (in the opinion of the Investigator).
- Presence of any of the following clinical conditions at the time of screening:
  - Drug or alcohol abuse, unstable medical disease (such as unstable angina or chronic obstructive pulmonary disease), active infectious disease (such as Hepatitis B or C or tuberculosis), current malignancy, unstable psychiatric illness (based on a prior psychiatric diagnosis that is unstable as determined by the subject's treating Psychiatrist) defined as psychosis or untreated major depression within 90 days of the screening visit, or any other condition that, in the opinion of the Investigator, might interfere with study conduct or interpretation of the study results.

## 6. Investigational Plan

### 6.1 Participant Identification Numbers

A participant ID Number will be assigned in sequential order to all patients who consent to screening. This unique 2-digit participant number for subjects will be used to identify the participant on all study forms and lab specimens.

### 6.2 Schedule of Activities

Refer to the protocol synopsis Schedule of Activities that summarizes the assessments to be conducted

#### 6.2.1 Screening Visit

All subjects will undergo a screening evaluation prior to the Baseline visit. This evaluation will include the following activities and will take about 2 hours to complete:

- An explanation of the purpose, procedures, potential risks and benefits of this study and informed consent will be obtained
- Demographics
- Review of the subject's medical and family history
- Review of concomitant medications
- Vital signs (blood pressure, heart rate and temperature)
- General physical examination
- Neurological examination (ALSFRS-R, MGH Upper Motor Neuron scale assessment (MGH UMN))
- Edinburgh Cognitive and Behavioural ALS Screen (ECAS)
- Collect blood sample for DNA for TSPO genotype
- Blood and urine collection for clinical laboratory assessments
- Blood and urine collection for research samples
- Urine pregnancy test for women of childbearing potential.
- Electrocardiogram (ECG)
- Forced Vital Capacity (FVC)
- A review of the inclusion/exclusion criteria to confirm that the subject is eligible to continue to the Baseline visit

#### *6.2.2 Baseline Assessments (Day 1, 2 and 3):*

The activities for the Baseline Assessments will be completed within 30 days of completing the Screening visit. Screening and Day 1 can occur on the same day.

Baseline assessments will include the following activities and will take Day 1-3 to complete, as listed in the schedule of activities. These assessments and subsequent activities will occur as an inpatient of Macquarie University Hospital. All assessments listed below must be completed prior to enrollment of the subject into the treatment phase of the study.

- Review of continuing ability to consent
- Vital signs (blood pressure, heart rate and temperature), height and weight
- Physical examination
- ECG

- Blood collection for clinical laboratory assessments (daily)
- Urinalysis (day 3)
- Blood and urine collection for research samples (daily)
- Urine pregnancy test (Day 1)
- Neurological exam (incl. ALSFRS-R and UMN Index)
- Brain MRI (Day 2)
- Brain PET Imaging (Day 2)
- Lumbar puncture for collection of CSF (Day 3)
- Review of concomitant medications
- Review of current medical conditions
- Review of adverse events related to lumbar puncture
- Repeat review of the inclusion/exclusion criteria

Once all Visit 1 activities have been completed and the Investigator determines that all eligibility criteria have been met, the subject may be enrolled into the study. Once enrolled, the subject will be enrolled in one of two dose levels of 3K3A-APC (15mg or 30mg).

#### *6.2.3 Inpatient Daily Assessments (Visit 4-10, Days 4-10)*

Administration of 3K3A-APC will occur as an inpatient of Macquarie University Hospital at 12 hourly intervals commencing Day 3 and continuing to Day 5.

Subjects will be assessed daily while inpatients in Macquarie University Hospital. The assessments are outlined in the schedule above and will include:

- Vital signs (Daily)
- ECG (Daily, excluding day 6 and 7)
- Clinical laboratory assessments (EUC, LFT, FBC, APTT, PT)
- Urinalysis (Day 4, 5,10)
- Research blood and urine samples (Daily, excluding day 6 and 7)
- Urine pregnancy test (Day 8)
- Physical examination (Day 8)
- Neurological examination (ALSFRS-R, MGH UMN scale) (Day 8)
- Repeat MRI Brain (Day 9)
- Repeat PET Imaging (Day 9)

- Repeat Lumbar puncture (Day 10)
- Assessment of adverse events (Daily)

Following completion of Day 10 assessments, the subject will be discharged home for follow up as an outpatient for the end of study visit (Visit 11).

#### *6.2.4 End of Study Assessment (Visit 11 Day 15)*

The end of study visit will be completed as an outpatient. End of study assessments will include:

- Vital signs
- ECG
- Physical examination
- Neurological examination (ALSFRS-R, MGH UMN Scale)
- Blood and urine collection for clinical laboratory assessments
- Blood and urine collection for research samples
- Assessment of adverse event

#### *6.2.5 Early termination visit*

All patients who discontinue early from the study should return to the clinic to complete the procedures for Visit 11. Study personnel should make every effort to conduct all protocol-specified procedures to complete the study.

## **7. Study Assessments**

### **7.1 Clinical Assessments**

#### *7.1.1 Vital Signs*

Blood pressure, heart rate and temperature will be measured at every visit via standard methods. Height and weight will be recorded at baseline.

#### *7.1.2 General Physical Examination*

At screening and baseline (Day 1), Visit 8 and Visit 11, a general physical examination will be recorded by the investigator including cardiac, respiratory, abdominal examination.

#### *7.1.3 Neurological Examination*

Standardised neurological examination will be performed by the principal investigator at screening, Visit 1, Visit 8 and Visit 11. This will include standardised assessments of UMN features such as tone, reflexes and primitive reflexes (plantar response). Assessment of motor function will be determined in standardised fashion (MRC grade, pinch grip and grip strength). ALSFRS-R and UMN Scale will be assessed and calculated.

### *7.1.3 Electrocardiograph*

A standard 12 lead ECG will be recorded at screening, baseline and each visit of the study (excluding day 6 and 7) via standard methods.

### *7.1.4 Forced Vital Capacity*

Forced vital capacity in the standing or seated position will be obtained via standard methods at screening.

### *7.1.5 Clinical Laboratory Tests*

Routine clinical laboratory tests indicated in the table below will be performed at screening and follow up visits according to the visit schedule. A central laboratory (Sonic) will be implemented in order to guarantee identical analysis methods, consistent normal ranges and thus common interpretation of laboratory changes. If not stated otherwise, venous whole blood will be collected in blood collection tubes (vacutainers).

The coagulation panel (PT/APTT) will be reviewed by the Investigator prior to lumbar puncture.

No more than 40 mL will be drawn at any visit, including both clinical and research blood samples (see 7.2.4 below).

CLINICAL LABORATORY TESTS	
METABOLIC PANEL	BLOOD COUNT
Sodium (Na)	White Blood Cell Count (WBC)
Potassium (K)	Red Blood Cell Count (RBC)
Chloride (Cl)	Hemoglobin (Hb)
Bicarbonate (HCO 3 )	Hematocrit (HCT)
Urea	Platelet Count (PLT)
Glucose	
Calcium (Ca)	
Creatinine (Cr)	
Bilirubin Total	
Albumin	
Total Protein	
Aspartate aminotransferase (AST)	
Alanine aminotransferase (ALT)	
Alkaline Phosphatase (ALP)	
Creatinephosphokinase (CPK)	
Iron studies (Fe, Ferritin)	
Prothrombin time (PT)	
Activated Partial Thromboplastin Time (APTT)	

As part of the clinical laboratory tests, urine will be collected for urinalysis at screening, day 3-5., day 10 and day 15.

A urine pregnancy test will be conducted at screening and prior to [F]FEMPA PET scan on Visit 1 and Visit 8.

All samples for laboratory analysis must be collected, prepared, labelled, and shipped according to the laboratory's requirements.

#### 7.1.6 Adverse Events

During each visit participants will be asked about adverse events. AEs will be recorded on an ongoing adverse event log.

#### 7.1.7 Concomitant Medications

All concomitant medications during hospitalization will be recorded on a log.

## 7.2 Other Assessments

### 7.2.1 TSPO Genotyping

A sample of venous blood will be collected at screening for DNA extraction to be used for TSPO genotyping to determine whether subjects have high affinity, mixed affinity or low affinity binding for the TSPO ligand according to established methods (10).

### 7.2.2 Microglial PET Imaging

Subjects will undergo [F] FEMPA PET imaging to assess the activation state of microglia in the brain. On Day 2 and Day 9 subjects will receive approximately 200 MBq of [F] FEMPA with dynamic brain scanning from time=0 to 50 minutes according to previously established protocols. Scanning time will be 50 minutes in total.

### 7.2.3 Brain MRI (ALS protocol)

Subjects will undergo a structural MRI brain scan on Day 2 and on Day 9 according to established protocols (9). At the discretion of the investigator and imaging staff, subjects who have presence of pacemakers, aneurysm clips, artificial heart valves, cochlear implants, metal fragments or foreign objects in the eyes, skin or body or any other known contra-indication to MRI may be advised not to complete a baseline (or follow-up) MRI scan, but these subjects may still participate in the study. MRI is being conducted to assess the structure of the brain, for co-registration with PET images as well as assessing the integrity of the blood brain barrier.

### 7.2.4 Biomic Blood and Urine samples

Whole blood (8 mL), serum (about 10 mL) and plasma (about 10 mL) will be collected to conduct proteomic, metabolomic and other analyses. Urine (about 10 mL) will be collected to conduct analyte analyses. Where possible the research blood samples will be collected in a fasted state (i.e., minimum of 8 hours since last meal/food intake) to ensure the quality of samples for future analyses. All research samples will be stored indefinitely for research purposes.

### 7.2.5 Lumbar Puncture for CSF Examination

The lumbar puncture (LP) will be performed under image intensifier by a qualified radiologist appointed by the investigator. A lumbar puncture for the collection of 10 mL of CSF will be conducted for all subjects at Visit 3 and Visit 10 unless there is evidence of clinically significant coagulopathy or thrombocytopenia that would interfere with the safe conduct of the procedure. The first 2 mL of CSF will be processed at the local laboratory facility to conduct standard analyses on cell count, protein and glucose levels. Subjects will be closely monitored during the procedure and following the procedure. The CSF samples will be stored indefinitely for research purposes for analytes relevant to inflammation and monocyte activation.

## 8. Study Medications

### 8.1 Study medication dose, packaging and labelling

3K3A-APC is supplied frozen in vials of 5mg at a concentration of 1.0mg/mL. Upon thawing, the sterile solution is clear and requires dilution in 0.9% sodium chloride for intravenous infusion. 3K3A-APC will be prepared for infusion by clinical trials pharmacist using aseptic technique. For the first treatment cohort, 3 vials of 3K3A-APC will be diluted to 100mL. For the second cohort, 6 vials of 3K3A-APC will be diluted to 100mL. See pharmacy manual for more information regarding study medication handling.

Infusion bags will be labelled by the clinical trials pharmacist with study name (3K3A-APC in ALS) and protocol number (ZZ-3K3A-202), patient name and study number, and medication name (3K3A-APC) and concentration.

### 8.2 Study medication administration

The study medication must be infused within 8 hours of preparation.

The 100mL of study medication will be administered by IV infusion over 15 minutes (by pump set to 400mL/hr). Five doses of study medication will be administered at 12 hourly intervals  $\pm$  1 hour starting on day 3 of hospitalization and finishing on day 5 of hospitalisation. Study drug should be flushed from infusion line with 0.9% sodium chloride.

If a hypersensitivity reaction develops, infusion is stopped immediately and no further doses of study medication will be administered.

### 8.3 Prohibited Concomitant Medications

Anticoagulant medications are prohibited during the treatment period, and for 7 days prior and 7 days post study drug administration. Anticoagulant medications include heparins, low molecular weight heparins, novel oral anticoagulants (e.g. dabigatran, rivaroxaban and apixaban), warfarin.

Medications that might interfere with monocyte activation such as systemic corticosteroids or immune suppressants are prohibited from screening visit until follow up at day 15.

It is preferred that subjects do not participate in clinical trials of other investigational interventions during the entire study.

All concomitant medications reported at the time of the screening visit and for the duration of the subject's participation should be recorded on the Concomitant Medication Log.

## 9. Subject Withdrawals

Subjects will be advised in the written informed consent forms that they have the right to withdraw from the study at any time without prejudice, and may be withdrawn at the investigator's or sponsor's discretion at any time. A subject

should be withdrawn from the study if the investigator considers it to be medically necessary, or if the subject withdraws consent. All reasons for subject withdrawals from the study will be recorded in the source documentation and appropriate eCRF.

## 10. Safety/Adverse Events

Site investigators and coordinators will be instructed to assess for adverse events at in-person study visits.

### 10.1 Adverse Event Definitions

#### Adverse Events (AE)

An AE is any undesirable experience occurring to a subject during a clinical trial, whether or not considered related to the investigational product.

Pre-existing conditions (i.e., undesirable experiences, signs or symptoms that begin prior to the Screening Visit) will be recorded on the medical history CRF page. These conditions will not be reported as an AE unless they worsen in intensity or frequency after the Screening Visit.

Treatment-emergent AEs are undesirable experiences, signs, or symptoms that begin or worsen in intensity or frequency at the time of or after the administration of study drug.

#### Serious Adverse Event (SAE)

An SAE is an AE that is fatal or life-threatening, or results in prolongation of hospitalization, persistent or significant disability/incapacity. A life-threatening AE is an AE that, in the view of the investigator, places the subject at immediate risk of death from the event, as it occurred. Important medical events that may not result in death, be life-threatening, or require hospitalization may be considered an SAE when, based upon appropriate medical judgment, they may jeopardize the subject and may require medical or surgical intervention to prevent one of the outcomes listed in this definition.

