#### 10.4 Recording of Adverse Events

Adverse events including clinically significant biological sample test abnormalities, whether observed by the investigator, elicited from or volunteered by the subject, should be recorded on the Adverse Event Log. This will include a brief description of the experience, the date of onset, the date of resolution, the severity, and seriousness and whether the event was related to participation in the research study.

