#### 10.5 Responsibilities for Reporting Serious Adverse Experiences

- The Investigator should notify the sponsor within 24 hours of his/her becoming aware of the occurrence of a serious adverse experience or suspected unexpected serious adverse reaction (SUSAR).
- The following information should be supplied if available at the time of the email or telephone call: subject number, subject age and gender, date of onset of event, event description, whether event required treatment, death and autopsy report, an identification of which criteria for a serious experience have been met, the Investigator's current opinion of the relationship between the event and study participation.
- The Investigator will comply with Macquarie University HREC regulations regarding the reporting of adverse experiences.

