### 12.2 Lumbar Puncture

The most common risks of a lumbar puncture are pain at the site and a temporary headache usually due to a small amount of CSF leakage around the needle insertion site. Lying down for a few hours after the test can make a headache less likely to occur. There is a slight risk of infection because the needle breaks the skin's surface, providing a possible portal of entry for bacteria. A temporary numbness to the legs or lower back pain may be experienced. There is a small risk of bleeding in the spinal canal. Subjects will have blood drawn at Screening to test for coagulopathies.

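### The SAE definition in section 10.1 lists a prolonged hospital stay but not a new admission, so some readmissions after the Day 10 discharge meet no listed criterion

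*Combined protocol and SAP*

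**What the plan says.** Section 10.1, under Serious Adverse Event, opens with the list of qualifying outcomes: "An SAE is an AE that is fatal or life-threatening, or results in prolongation of hospitalization, persistent or significant disability/incapacity". Its last sentence adds a discretionary route: "Important medical events that may not result in death, be life-threatening, or require hospitalization may be considered an SAE", provided that medical judgment finds the patient may be put in jeopardy and may need intervention to avert one of the listed outcomes.

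The schedule then takes patients out of hospital before follow-up ends. Section 6.2.3: "Following completion of Day 10 assessments, the subject will be discharged home for follow up as an outpatient". Section 6.2.4: "The end of study visit will be completed as an outpatient". That visit is on Day 15.

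Two procedures depend on the definition. Section 10.4 has the adverse event log record "the severity, and seriousness and whether the event was related to participation in the research study". Section 10.5 sets the clock, "The Investigator should notify the sponsor within 24 hours", and asks the report to include "an identification of which criteria for a serious experience have been met".

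**The concern.** The first sentence of the definition names four outcomes: death, threat to life, a prolonged hospital stay, and disability. An adverse event that brings a patient back into hospital is not among them. The last sentence widens seriousness to events that might not need hospitalization, which makes sense only if needing it already counts. The two sentences do not agree.

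The schedule gives the disagreement practical effect. While patients are inpatients, the prolonged-stay outcome can apply. Once they are discharged it cannot, and five days of follow-up remain.

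Safety is the primary outcome (section 3.1). A readmission would still be logged under section 10.4 and listed under section 15.2, so the event is not lost. What is at stake is whether it is labelled serious and whether the sponsor hears within 24 hours. Two careful readers could classify the same readmission differently, depending on which sentence they follow. The 30 mg cohort follows the 15 mg cohort, so prompt and consistent classification in the first cohort matters.

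**Working it through.** The documents state no figure on this point, so there is none to reproduce. The main check is a comparison of the text; the arithmetic only gives scale.

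**1. A readmission on Days 11 to 15 that is neither fatal, life-threatening nor disabling, tested against the definition**

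| Criterion in section 10.1 | Met? |
|---|---|
| Fatal | No, by assumption |
| Life-threatening | No, by assumption |
| Prolonged hospital stay | No: the stay ended on Day 10 |
| Disability or incapacity | No, by assumption |
| Important medical event | Only if the investigator so judges; needs jeopardy and possible intervention to avert a listed outcome |

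The protocol offers a possible example. The second lumbar puncture is on Day 10, the day of discharge (section 6.2.3), and section 12.2 says "The most common risks of a lumbar puncture are pain at the site and a temporary headache". If such a headache led to an uncomplicated readmission, the report required by section 10.5 would have no listed outcome to name.

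**2. Whether another section supplies the criterion**

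- Section 10.5 asks which criteria were met but does not list them.
- Section 13.4 expects hospital admissions during the study, since it names their summaries as records open to review, but it does not classify them.
- Section 13.1 is a general statement of compliance with GCP and ICH.

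None adds a new admission to the list.

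**3. Exposure to the gap**

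Inputs: first dose on Day 3 and discharge on Day 10 (section 6.2.3), end of study on Day 15 (section 6.2.4), 16 patients in two cohorts of 8 (synopsis; section 2).

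- Outpatient days, Days 11 to 15: 5.
- Calendar days, Day 3 to Day 15 inclusive: 13. Share: 5/13 = 38%.
- As elapsed time: (15 − 10)/(15 − 3) = 5/12 = 42%.
- Patient-days: 16 × 5 = 80 of 16 × 13 = 208.

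**4. Chance of at least one such readmission**

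The documents give no rate. Let p be an assumed per-patient probability of a readmission that meets no other listed criterion, with patients independent. Then P(at least one in 16) = 1 − (1 − p)^16.

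| Assumed p | P(at least one in 16) |
|---|---|
| 1% | 15% |
| 2% | 28% |
| 5% | 56% |
| 10% | 81% |

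**5. Effect of one changed label**

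These are exact Clopper-Pearson two-sided 95% intervals, the method named in section 15.1. For x of n, the lower limit is the 2.5% quantile of Beta(x, n − x + 1), set to 0 when x = 0. The upper limit is the 97.5% quantile of Beta(x + 1, n − x).

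| Patients with an SAE | Proportion | 95% CI |
|---|---|---|
| 0/8 | 0% | 0 to 36.9% |
| 1/8 | 12.5% | 0.3 to 52.7% |
| 0/16 | 0% | 0 to 20.6% |
| 1/16 | 6.3% | 0.2 to 30.2% |

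**The case against.** The strongest reply is that the definition, read as a whole, points the right way. If the last sentence presupposes that needing hospitalization counts, a sensible investigator will treat a readmission as serious. The important-medical-event clause does not exclude events that need admission, and many would qualify under it. Other safeguards exist: conduct under GCP and ICH (section 13.1), the duty to follow the ethics committee's reporting rules (section 10.5), and an independent monitor who checks that adverse events are reported on time (section 17). The trial is at a single centre, all dosing is inpatient, and the sponsor and the site are the same university.

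Much of this is fair, and it narrows the gap. It does not close it. The clause is discretionary, and none of the safeguards amends the written list on which the seriousness label and the 24-hour notice depend. That the last sentence implies a criterion the first omits is the inconsistency itself.

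Three further points stand as limits:

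- The assumed probabilities have no anchor in the documents, and a result of 15% to 81% excludes little.
- The intervals in step 5 would be the same for any single misclassified SAE, and section 15.2 does not expressly name an SAE proportion among its summaries.
- Nothing in the documents says that post-puncture headache leads to readmission; section 12.2 calls it temporary. The example shows how the gap could arise, not how often.

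**Conclusion.** The concern holds: the definition is wrong as written and should be fixed. Its first sentence omits new admission, its last sentence presupposes it, and no other section supplies it. Followed literally, a readmission between the Day 10 discharge and Day 15 can go without a serious label unless it is fatal, life-threatening, disabling or judged medically important.

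The size that the documents support is a five-day outpatient window in at most 16 patients who complete the planned stay. A patient who leaves hospital early could be exposed for longer. The same wording also covers an admission between screening and Day 1, but such events precede dosing and are not treatment-emergent. The conclusion does not depend on the assumed readmission probabilities. No planned analysis is invalidated; the harm is ambiguous classification and possibly missed expedited notice, in a trial whose primary outcome is safety.

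**What to change.** Amend the first sentence of the SAE definition in section 10.1 so that the hospital criterion covers an AE that *requires inpatient admission or prolongs an existing one*, and leave the other outcomes as they are. The list then agrees with its own last sentence and with the outpatient period in sections 6.2.3 and 6.2.4, and section 10.5 has a criterion to name.

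Check that the SAE report carries the same criterion; that form is not among the documents, so its present content is unknown.

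The cost is one sentence, one matching report field, and perhaps slightly more SAE reports. No dose, visit or procedure changes.
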